3.6. Procedures

In table 1. Detailed follow up evaluations are described.

Table 1. Description of the evaluations to be done during the trial.

Follow up table				
Day	General activity	Specific activity	Responsible	Result
0	Base line diagnoses	Initial Clinical evaluation	Medical doctor of the study	Evaluating inclusion and exclusion criteria. Signing informed consent form
		Blood samples	Nurse Lab tech	Laboratory report: hemogram, creatinine, phosphorus, AST, ALT HIV ELISA, HB Surface antigen antibodies
		SARS-CoV-2 RT-PCR sampling	Respiratory therapist or nurse	Result of SARS-CoV-2 RT-PCR
		SARS-CoV-2 IgM and IgG antibodies	Nurse Lab tech	Result of IgM and IgG antibodies
		b-HCG sampling in women	Nurse Lab tech	Report of b-HCG
20	Visit 1	Clinical evaluation	Medical doctor of the study	Clinical record and eCRF for clinical evaluation, adherence, and adverse events

40	Visit 2	Blood sample for: SARS-CoV2 IgM, IgG antibodies and blood chemistry	Nurse Lab tech	Laboratory report of SARS-CoV2 IgM, IgG antibodies and creatinine
		Clinical evaluation	Medical doctor of the study	Clinical record and eCRF for clinical evaluation, adherence, and adverse events
60	Visit 3	Blood samples	Nurse Lab tech	hemogram, creatinine, phosphorus, AST, ALT HIV ELISA, HB Surface antigen antibodies b- HCG in women
		SARS-CoV-2 RT-PCR sampling	Respiratory therapist	Result of SARS-CoV-2 RT-PCR
		Clinical evaluation	Medical doctor of the study	Clinical record and eCRF for clinical evaluation, adherence, and adverse events
75	Visit 4	Blood samples	Nurse Lab tech	Laboratory report of SARS-CoV2 IgG
		Clinical evaluation	Medical doctor of the study	Clinical record and eCRF for clinical evaluation,
		End of follow up and communication to study subject	Clinical coordinator	Minutes

During follow up to any participant who develop COVID-19 related symptoms at any time after randomization given by two or more of the following: Body temperature higher than 38 Celsius, cough of recent onset (in the previous 10 days), dyspnea,odynophagia, malaise, fatigue, acute diarrheal disease, ageusia, dysgeusia, anosmia or hyposmia, an RT-PCR will be performed within the next 5 days and will be repeat it if the result is negative and the symptoms persist. This RT-PCR will be performed at every of the centers of the study and will request the patient the immediate report of the symptoms through an app or via phone call. In case of a positive RT-PCR the infection

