The hazard ratio will be estimated by comparing the risk of infection in the intervention group (TDF/FTC + EPP), with the risk in the control group (placebo + EPP), with a confidence interval of 95 %, using a univariate Cox regression model.

If necessary, adjustment will be made for variables that may affect the occurrence of the primary outcome and that are not balanced between the intervention group and the placebo group; The need for adjustment with an OR greater than 1.5 will be considered for dichotomous categorical

variables, such as sex; or if there are differences between the groups greater than 0.25 of the standard deviation for continuous variables such as age, adherence to pharmacological intervention or EPP, and hours of exposure to the COVID area. For the calculation of the adjusted hazard ratio, a multivariate Cox proportional hazards model will be used, if the proportionality assumption is met, or an extended Cox model if this assumption is not met.

For secondary outcomes

-The proportion of incidence of total adverse effects in each group will be determined at day 60 after randomization, estimated as the cumulative incidence using the Kaplan Meier method.

The hazard ratio ("Hazard Ratio") will be estimated by comparing the risk of adverse events in the intervention group (TDF/FTC + EPP), with the risk in the control group (placebo + EPP), with a confidence interval of 95%, using a univariate Cox regression model.

Additionally, the same analysis will be performed for serious adverse events.

- The proportion of incidence of discontinuation of the intervention in each group, for any reason, will be determined at day 60 after randomization, estimated as the cumulative incidence using the Kaplan Meier method.

The hazard ratio will be estimated by comparing the discontinuation of the intervention in the intervention group (TDF/FTC + EPP), with the risk in the control group (placebo + EPP), with a confidence interval of 95 %, using a univariate Cox regression model.

- It will be determined as the difference in the mean or median (according to the distribution of the data) of the percentage in which the individuals were adherent

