Grade 2 to 4 laboratory abnormalities seen in the iPrEx and Partners PrEP assays are rare, generally less than 5% (80-82). Six subjects in the TDF-containing arms of the Partners PrEP trial discontinued the trial due to an increase in serum creatinine, compared with no discontinuation in the placebo group. One subject in the TDF/FTC arm of the iPrEx trial discontinued due to an increase in serum creatinine and another subject discontinued due to low serum phosphorus. Grades 2-3 proteinuria (2-4 +) and / or glycosuria (3+) occurred in less than 1% of TDF/FTC-treated subjects in the iPrEx trial and the Partners PrEP trial.

- Alterations in bone mineralization.

In some clinical trials evaluating TDF/FTC in pre-exposure prophylaxis for HIV for 18 months, decreases in bone mineral density (BMD) have been observed and described in uninfected individuals. In the iPrEx trial, a substudy of 503 subjects found mean changes from baseline in BMD

ranging from -0.4% to -1.0% in total hip, spine, femoral neck, and trochanter in the TDF/FTC group compared to the placebo group, who returned to their baseline values after PrEP was discontinued. 13% of TDF/FTC treated subjects, in contrast to 6% of placebo treated subjects, lost at least 5% of BMD in the spine during treatment. Bone fractures were reported in 1.7% of the TDF/FTC group compared to 1.4% in the placebo group, however, no correlation was observed between BMD and fractures. (96)

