Telephone contact potential volunteers		X							Registration with participants interested in being included	Record of execution of the procedure and database in Excel.
Informed consent		X							Signed informed consents	Database of study subjects recruited
Clinical CRF history		X	X	X	X	X			Clinical History of the study subject	Clinical CRF Registry
Clinical Assessment		X	X	X	X	X			Clinical History of the study subject	Clinical CRF Registry
Supervised first dose of drug administration		x							Confirmation of taking at least 1 dose of TDF/FTC or placebo	Drug dispensing registration document
Taking of RT-PCR for SARS-CoV-2		X			X				Positive or negative diagnostic test result	Laboratory report
Antibody IgG - IgM SARS - CoV-2 testing		X		x		x			Positive or negative diagnostic test result	Laboratory report
Sampling for CBC, Creatinine, AST, ALT, P, HIV ELISA, Acs anti HBsAg and		X		X		X			Results of liver, kidney, hematological, electrolyte function tests and pregnancy status in the	Laboratory report

Beta HCG in women									case of participating women.	
Verification of eligibility criteria		X							Determination of the inclusion or not of the participant	Check list
Randomization		X							Random Assignments to Intervention or Placebo	Database
CRF Adverse Events Registry			X	X	X	X			History of adverse events	CRF registration document Adverse event
Finish follow-up and communication to the study subject							X		Formal follow-up completion record	Completion certificate document
Systematization and organization of data							X		Office registry refined with data extracted from the clinical trial	Systematized database
Results analysis								X	Outcome estimates, statistical associations, causality inferences and risks of bias and limitations	Document with results, tables, graphs and data of the study
Communication and publication of results and conclusions.								X	National and international communication of the results and	Two articles of scientific publication, report of results and recommendation

									conclusions of the study	ns of the researchers
--	--	--	--	--	--	--	--	--	-----------------------------	--------------------------

9. Budget

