9.1 Technical services

No.	Item	Site	Justification	Quantity	Unit value (cop)	Subtotal (cop)
1	Civil liability policy for volunteers and clinical trial personnel	Pontificia Universidad Javeriana	Regulatory agency requires a liability protection for both, volunteers and clinical trial personnel regarding risks during COVID-19 pandemic.	1	\$ 96,101,872.44	\$ 96,101,872.44
2	Clinical laboratory tests (Creatinine; CBC; ALT; AST; BHCG in women, antiHBS; HIV, IgG Antibodies; Serum phosphorus, CRP)	Pontificia Universidad Javeriana	Laboratory exams required at baseline and follow-up	1	\$ 535,959,372.00	\$ 535,959,372.00
3	rtPCR for symptomatic volunteers (7,5%)	Pontificia Universidad Javeriana	rtPCR for follow-up 1, for volunteers who develop respiratory symptoms (estimated of 7.5%)	71	\$ 250,000.00	\$ 17,750,000.00
4	Laboratories for follow-up 2 (creatinine and antibodies)	Pontificia Universidad Javeriana	Laboratory tests for 950 volunteers	1	\$ 50,071,650.00	\$ 50,071,650.00
5	RtPCR including transport media for follow-up 2.	Pontificia Universidad Javeriana	Laboratory tests. It is estimated that 7.5% of volunteers will develop symptoms that require rtPCR. Services will be provided by recruitment sites	71	\$ 250,000.00	\$ 17,750,000.00
6	Laboratory tests (Creatinine, CBC, ALT, AST, BHCG for women (80% of volunteers) and rtPCR for all subjects.	Pontificia Universidad Javeriana	Laboratory tests for each participant (80% women; 20% men)	1	\$ 285,512,810.00	\$ 285,512,810.00
7	IgG antibody tests for follow up 4	Pontificia Universidad Javeriana	IgG antibody tests for follow up 4	1	\$ 43,320,000.00	\$ 43,320,000.00
8	Recruitment services	Pontificia Universidad Javeriana	Recruitment costs per volunteer including PPE + workhours of pharmaceutical chemist, respiratory therapist, assistant nurse, and laboratory assistant	950	\$ 105,699	\$ 100,414,240
						\$1,146,879,944

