Diastolic blood pressure	Quantitative/discrete	Diastolic blood pressure	Diastolic blood pressure in mmHg
Creatinine	Quantitative/continuous	Serum creatinine concentration (mg/dl).	Serum creatinine concentration (mg/dl).
Creatinine rise	Qualitative/nominal	Severity of creatinine rise	0-Normal 1-Grado 1 2-Grado 2 3-Grado 3 4-Grado 4
IgG for SARS-CoV-2	Qualitative/dichotomous	Result of serology test for SARS-CoV-2 (only for follow-up 2)	0- Negative 1- Positive
Data to be collected in follow-up 3			
Platelets	Quantitative/discrete	Number of platelets in complete blood count (CBC)	Number of platelets per microliter (Cels/ μ l).
Thrombocytopenia	Qualitative/nominal	Severity of thrombocytopenia	0-Normal 1-Grade 1 2-Grade 2 3-Grade 3 4-Grade 4
Hemoglobin (Hb)	Qualitative/continuous	Hemoglobin concentration in CBC	Hb (g/dl).
Anemia	Qualitative/nominal	Classification of severity of anemia	0-Normal 1-Grade 1 2-Grade 2 3-Grade 3 4-Grade 4
Lymphocytes	Quantitative/discrete	Number of lymphocytes in complete blood count (CBC)	Number of lymphocytes per microliter (Cels/ μ l).
Lymphopenia	Qualitative/nominal	Classification of severity of lymphopenia	0-Normal 1-Grade 1 2-Grade 2 3-Grade 3 4-Grade 4
Neutrophils	Quantitative/discrete	Number of neutrophils in complete blood count (CBC)	Number of neutrophils per microliter (Cels/ μ l).
Neutropenia	Qualitative/nominal	Classification of severity of neutropenia	0-Normal 1-Grade 1 2-Grade 2 3-Grade 3 4-Grade 4
Aspartate aminotransferase (AST)	Quantitative/continuous	AST concentration in international units per liter (UI/l)	AST (UI/l).
Aspartate aminotransferase elevation	Qualitative/nominal	Severity of elevation of AST	0-Normal 1-Grade 1 2-Grade 2 3-Grade 3 4-Grade 4
Alanine aminotransferase (ALT)	Quantitative/continuous	ALT concentration in international units per liter (UI/l)	ALT (UI/l).
Alanine aminotransferase elevation	Qualitative/nominal	Severity of elevation of ALT	0-Normal 1-Grade 1 2-Grade 2 3-Grade 3 4-Grade 4

Pregnancy test	Qualitative/dichotomous	Applicable only to women. Result of quantitative serum Beta-HCG test regarding upper reference value for non-pregnant women.	0- Negative 1- Positive
RT-PCR SARS-CoV-2	Qualitative/dichotomous	Detection of SARS-CoV-2 by RT-PCR de	0- Undetectable 1- Detectable
Data to be collected only in Follow-up 4			
Follow-up date	Quantitative/continuous	Follow-up date	Day/month/year

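### Serum phosphorus is drawn at day 60 but has no numeric data field, grade or planned comparison by arm, and adverse events in days 61 to 75 have conflicting capture instructions and no planned incidence estimate

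*Combined protocol and SAP*

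**What the plan says.** **Phosphorus.** Table 1 in section 3.6 schedules phosphorus at day 0 and again at Visit 3 (day 60), where the panel reads "hemogram, creatinine, phosphorus, AST, ALT HIV ELISA, HB Surface antigen antibodies b- HCG in women". At Visit 2 the only chemistry result it names is creatinine. Table 6 (study schedule) has a row beginning "Sampling for CBC, Creatinine, AST, ALT, P, HIV ELISA, Acs anti HBsAg and", marked at recruitment, Visit 2 and Visit 4. In Appendix 3 the list headed "Data to be collected in follow-up 3" names blood counts, AST, ALT, a pregnancy test and RT-PCR, but not phosphorus. Section 5.1.1 lists hypophosphatemia among the post-marketing reactions to tenofovir. It also reports that in one prevention trial "another subject discontinued due to low serum phosphorus".

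**Adverse events.** Table 6 has a row "CRF Adverse Events Registry" marked at all four visits. Table 1 names adverse events at days 20, 40 and 60 but not at day 75. In Appendix 3 the adverse-event fields sit under the heading for Follow-ups 1 to 3. The list headed "Data to be collected only in Follow-up 4" contains a date, symptoms, vital signs and IgG only. Section 4 states: "The proportion of incidence of total adverse effects in each group will be determined at day 60 after randomization". It applies the same analysis to serious events.

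**The concern.** Safety is half of the general objective, and section 4.1 explains that the trial will have no data monitoring committee. The CRF and the SAP therefore carry most of the safety evaluation.

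If the data dictionary is followed as written, a safety analyte that the trial already pays to draw leaves no values to compare between arms. A field that was never collected cannot be recovered at the analysis stage. Phosphorus matters enough to the plan to be an exclusion criterion, and section 5.1.1 names its depletion as a reported reaction to the study drug.

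The second gap is similar. Two parts of the plan tell sites different things about adverse events at the final visit, and anything recorded there has no planned incidence estimate.

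**Working it through.** The plan states no figure on this point to reproduce. The check sets the passages side by side.

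**Step 1. Follow phosphorus through the plan.**

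| Place | Phosphorus |
|---|---|
| Table 1, day 0 and day 60 | Drawn |
| Table 6 | Panel marked at recruitment, Visit 2, Visit 4 |
| Appendix 3, screening | Yes/no exclusion item; no number |
| Appendix 3, Follow-ups 2, 3 and 4 | Absent |
| Laboratory grading table, section 6.3 | No row (ALT/AST, hemoconcentration, anemia, lymphocytes, neutrophils, platelets and creatinine have one) |
| Section 4 | No phosphorus analysis |
| Budget 9.1, item 2 | Named; justified for both baseline and follow-up |
| Budget 9.1, item 6 | Absent: "Laboratory tests (Creatinine, CBC, ALT, AST, BHCG for women (80% of volunteers) and rtPCR for all subjects" |

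Section 3.6.8 says results are read against the laboratory's own range together with the protocol's severity criteria. For phosphorus there are no such criteria. There is also no single cut-off for a low value: section 3.2 excludes below 2.5 mg/dl, while Appendix 3 uses the laboratory's lower reference value. These two need reconciling as well.

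**Step 2. Check the Table 6 reading.** In Table 6 the RT-PCR row falls at Visit 3 and the antibody row at Visits 2 and 4, where Table 1 also puts them. The columns are therefore read correctly, and the disagreement over the safety panel is real.

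**Step 3. Size of the phosphorus gap.** Numeric fields for phosphorus in Appendix 3: 0. Day 60 values affected: up to 950, or 950 × 0.90 = 855 if losses reach the 10% allowed for in section 3.4. Because the baseline number is missing too, a day 60 field alone would not give change from baseline.

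**Step 4. Budget.** Per participant, item 2 is 535,959,372 / 950 = COP 564,168 and item 6 is 285,512,810 / 950 = COP 300,540. Taking off one RT-PCR at the 250,000 shown in items 3 and 5 leaves 50,540 in item 6. No unit price for phosphorus is given, so these sums cannot show which draws item 2 funds.

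**Step 5. Follow adverse events past day 60.**

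| Place | Visit 4 (day 75) |
|---|---|
| Table 6 | Adverse-event form scheduled |
| Section 6.2 | Assigned researcher records all events on a dedicated form |
| Table 1 | Not named |
| Appendix 3, Follow-up 4 | No field |
| Appendix 3, definition | Limited to the time on product |
| Section 4 | Incidence at day 60; no later horizon named |

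Days outside the stated incidence horizon: 75 − 60 = 15, and 15 / 75 = 20% of calendar follow-up. This is a share of time, not of events.

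**The case against.** Three stronger readings are tempting, and the documents do not support them.

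- *Phosphorus has no follow-up budget.* Item 2 of section 9.1 names serum phosphorus and covers baseline and follow-up. Only item 6, the line that matches the day 60 panel, omits it.
- *There is no form for adverse events after day 60.* Table 6 schedules one at Visit 4, and section 6.2 requires all events to be recorded with date, duration and severity. The Visit 4 cell in Table 1 ends in a comma, so text may be missing there. What exists is a contradiction with Table 1 and Appendix 3, not a uniform absence.
- *Low phosphorus cannot be assessed.* Section 6.1 counts abnormal laboratory findings as adverse events, a study physician reads each result, both event lists end in an open category, and proximal tubulopathy is a coded serious event.

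Other points also have force. A day 60 horizon fits a 60-day treatment and is a recognised on-treatment choice. The adverse-event hazard ratio has no stated cut-off day, so the missing estimate is firm only for cumulative incidence. The reported stopping for low phosphorus was one subject, and section 5.1.1 cites a large prevention trial with no significant difference in phosphorus abnormalities. It also says that the excess of gastrointestinal effects and fatigue came mainly in the first month. The Follow-up 3 list omits the day 60 HIV and anti-HBs results too, so it may not be exhaustive.

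What remains is that reporting through an open category depends on individual judgement without a common threshold. It does not give comparable rates by arm.

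**Conclusion.** The point holds as a gap in the data dictionary, the schedule and the safety analysis. As written, there is no systematic capture, uniform grading or planned between-arm comparison of phosphorus, for up to 950 day 60 values, and the visit at which it is drawn is contradictory. Adverse events in days 61 to 75 have conflicting capture instructions and no planned incidence estimate. How many events fall in those 15 days cannot be judged from the documents.

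The conclusion assumes that Appendix 3 defines what the CRF will hold. If the actual CRF already has a numeric phosphorus field, what remains is grading, analysis and the conflict between Tables 1 and 6. Phosphorus is not a named endpoint, and the primary analysis and sample size are not affected. This is a cheap improvement that should be made before data collection.

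**What to change.** 1. Add numeric phosphorus to Appendix 3 at baseline and at the follow-up draw. Add a severity scale chosen by the sponsor to Appendix 3 and the laboratory grading table.
2. In section 4, compare change from baseline and the frequency of low values by arm.
3. Reconcile the visit of the phosphorus draw between Table 1 and Table 6, and the two screening definitions of a low value.
4. Add adverse-event and serious-adverse-event items to the Follow-up 4 list and to the Visit 4 row of Table 1, to match Table 6. Word the Appendix 3 definition so that it covers the period after the last tablet.
5. Keep the day 60 on-product analysis and add a summary by arm of all events through Visit 4. State the cut-off day for the adverse-event hazard ratio.
6. State which visits budget item 2 funds, given that item 6 omits phosphorus.

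The cost is a few CRF fields, one more safety table and possibly a small assay cost. The blood draw and the Visit 4 clinical evaluation are already planned.
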